The primary efficacy endpoint is the annualized change in new HO volume (as assessed by WBCT). The change in new HO volume is calculated by summing the increase in HO volume across all body regions for which new HO has occurred where the increase in HO volume per region is defined as the square-root of the volumetric increase in that region. The square-root transformation is used to reduce the influence of outliers. Transformation of volumetric changes has been used in related contexts. For example, a log transformation has been used to model volumetric increases in the kidneys of subjects with autosomal dominant polycystic kidney disease^{1,2}. The change in new HO volume is modeled using a Bayesian compound Poisson distribution. The Bayesian compound Poisson distribution assumes that the change in new HO volume can be modeled as a compound distribution of the number of body regions with new HO, K , and the new HO volume per region where new HO has occurred, Z . The number of body regions with new HO in subject i for WBCT scan j with duration w_{ij} (the time between scan j and the previous scan) is distributed as

$$K_{ij} \sim \text{Pois}(\lambda_{i,j} * w_{ij} * \theta_{1,t(ij)});$$
$$\log(\lambda_{i,j}) = \log(\lambda_i) + \beta_1 X_{1,i} + \beta_2 X_{2,i,j}$$

The subject-level rate λ_i follows a gamma distribution and accounts for potential correlation in measurements from the same subject; $t(ij)$ is an indicator function equal to 1 if the subject was on treatment at the time of the j th WBCT scan and 0 if the subject was not on treatment. Therefore, the marginal distribution of the number of body regions with new HO follows a negative binomial distribution, which requires much less restrictive assumptions than a Poisson distribution and does not tend to result in an underestimate of the variance.

Letting $\theta_{1,0} = 1$, the variable $\theta_{1,1}$ is the multiplicative effect of palovarotene treatment on the rate of body regions with new HO. Covariates are included in the analysis of the number of body regions with new HO to adjust for potential explained differences in the rate of new HO based on the subject's sex, $X_{1,i}$, and age at time of scan, $X_{2,i,j}$. Age at the time of scan is represented as a factor variable with 0 for <18 years old and 1 for ≥ 18 years old. Covariate effects $\exp(\beta_1)$ and $\exp(\beta_2)$ are multiplicative effects of sex and age on the rate of body regions with new HO.

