The new HO volume (square-root of the volumetric increase in that region) in region r , $\sqrt{Z_{ijr}}$, where new HO has occurred for subject i in scan j is assumed to be distributed as:

$$\sqrt{Z_{ijr}}/1000 \sim N\left(\alpha * \alpha_r * \theta_{2,t(ij)}, \frac{\alpha_r^2}{\tau_{t(ij)}}\right).$$

The scale of new HO volume is modeled in the thousands. Letting $\theta_{2,0} = 1$, the variable $\theta_{2,1}$ is the multiplicative effect of palovarotene treatment on the new HO volume conditional on new HO occurring. The α_r are region-specific variables that contribute to the mean of new HO and the variance; the restrictions $\alpha_r = \alpha_{r'}$, where r and r' are a left and right region pair are included, i.e., right chest and left chest, right arm and left arm, right hip and left hip, and right lower leg and left lower leg. The precision variables, τ_0 and τ_1 , introduce flexibility by allowing variability to differ between new HO volume in treated subjects and untreated subjects.

The prior distributions for the variables in the Bayesian compound Poisson distribution are the following:

$$\begin{aligned}\lambda_i &\sim \text{Gamma}(a, \text{scale} = b) \\ \beta_1, \beta_2 &\sim N(0, 2^2) \\ a, b &\sim \text{Gamma}(1, 1) \\ \alpha &\sim N(0, 1) \\ \alpha_r &\sim \text{Unif}(0, 4) \\ \tau_0, \tau_1 &\sim \text{Gamma}(1, 0.01) \\ \theta_{1,1}, \theta_{2,1} &\sim \text{Unif}(0, 2).\end{aligned}$$

All gamma distributions are parameterized as the shape and rate, except as noted for λ_i . The primary efficacy analysis comparing the annualized change in new HO volume between subjects treated with palovarotene and untreated subjects is performed by calculating the ratio of the annual mean change in HO volume in palovarotene treated subjects to untreated subjects using the Principal FAS and assuming missing at random.

In this SAP, new HO is deemed to be present in a body region if the volume of net new HO is greater than zero, i.e., the change in volume of HO in a region between two timepoints is positive. (Volumes of individual lesions are not assessed; the net volume of HO in a body region is reported.). Any regions with amounts of new HO $< 0 \text{ mm}^3$, i.e., reductions in the volume of HO over time (which can happen due to bone remodeling or measurement variability), will be represented as having no new HO and the volumes will be set to zero in the analysis.

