For these reasons, while acknowledging that it is post-hoc, the sponsor believes that the Bayesian compound Poisson analysis without the square-root transformation is the more appropriate analysis of the primary endpoint, relative to the Bayesian compound Poisson analysis with the square-root transformation. The Bayesian analysis without square root transformation is referred to as the analysis of primary interest.

When performed without the square-root transformation, the new HO volume in region r , Z_{ijr} , where new HO has occurred for subject i in scan j is assumed to be distributed as:

$$Z_{ijr}/1000 \sim N\left(\alpha * \alpha_r * \theta_{2,t(ij)}, \frac{\alpha_r^2}{\tau_{t(ij)}}\right).$$

The prior distributions for the variables in this Bayesian compound Poisson distribution are the following:

$$\begin{aligned} \lambda_i &\sim \text{Gamma}(a, \text{scale} = b) \\ \beta_1, \beta_2 &\sim N(0, 2^2) \\ a, b &\sim \text{Gamma}(1, 1) \\ \alpha &\sim N(0, 10^2) \\ \alpha_r &\sim \text{Unif}(0, 4) \\ \tau_0, \tau_1 &\sim \text{Gamma}(1, 100) \\ \theta_{1,1}, \theta_{2,1} &\sim \text{Unif}(0, 2). \end{aligned}$$

The Bayesian compound Poisson model will be fitted using the R statistical computing language and environment. The R programs will be run using v3.5.0 or later; packages used, including version number, will be identified in the CSR.

Additional supportive analyses including the weighted mixed linear effect (wMLE) analysis with and without the square-root transformation will also be performed. The wLME analysis without the square-root transformation was previously the primary efficacy analysis, before the Bayesian compound Poisson analysis was added in Amendment 1 of the protocol. This wLME analysis without square-root transformation is referred to as the alternative analysis of primary interest.

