Ninety-nine palovarotene-naïve subjects with the R206H ACVR1 mutation were enrolled into the current trial and are to be followed for 2 years. There were to be three early interim efficacy analyses and one final analysis. Futility was declared at the second interim analysis, but the study continued. The final analysis for Part A will occur when all subjects have completed 2-year follow-up. (Note that, as described, due to the prolonged palovarotene interruption prior to the completion of Part A, IA3 is designated the final analysis.)

The first interim analysis was to take place when approximately 35 MOVE subjects complete 1 year of follow-up with the second and third interim analyses occurring when all subjects in the Principal EP have the opportunity to have complete (i.e., have WBCT data) 12 months and then 18 months of follow-up, respectively. It was assumed that the full NHS dataset will be available at the first interim analysis. The amount of statistical information at each interim analysis can be approximated by the sum of the follow-up in each study divided by the total expected. The total follow-up expected across the NHS and the MOVE Trial is 317.5 years (NHS: 45*1.5 years + 45*2.0 years; MOVE: 80*2.0 years). Assuming eight subjects enroll in the MOVE study per month, the percentage of subject follow-up for each analysis is summarized in Table 7 where values with an asterisk indicate approximate information based on expected accrual rates and total planned accrual in the Principal EP.

Table 7. Observed MOVE Follow-up at Each Planned Analysis

Analysis	Observed MOVE follow-up	Percentage of follow-up available
Interim #1	35 subjects with 12 months *45 subjects with 6 months	66%
Interim #2	*80 enrolled subjects with 12 months *35 subjects with 18 months	80%
Interim #3	*80 enrolled subjects with 18 months *35 subjects with 24 months	92%
Final	80 enrolled subjects with 24 months	100%

Using these percentages, the alpha level threshold used to determine treatment effect significance at each analysis was derived using the Lan-DeMets alpha-spending function with O'Brien-Fleming parameterization and assuming a one-sided, overall type I error rate of 2.5%. The one-sided significance thresholds are 0.0058, 0.0103, 0.0156, and 0.0190 for the first, second and third interim analyses and the final analysis, respectively, in the scenario above.

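### The volume half of the compound Poisson model has no subject-level term, so θ2 and, to a lesser degree, γ would be overconfident if a subject's HO volumes are positively correlated, and the described simulation does not test this

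*SAP*

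**What the plan says.** SAP 2.4.4 splits the outcome into a count of body regions with new HO and a volume for each such region. The treatment ratios are θ1 for the region rate and θ2 for volume given new HO. The decision quantity is the posterior probability that γ = θ1 × θ2 is below 1.

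- **Count half.** The subject rate λ_i has a gamma distribution and "accounts for potential correlation in measurements from the same subject". As a result "the marginal distribution of the number of body regions with new HO follows a negative binomial distribution", which the SAP gives as the reason the variance is not understated. Sex and age also enter here: "Covariates are included in the analysis of the number of body regions with new HO".
- **Volume half.** The volume for subject i, scan j, region r is normal with mean α·α_r·θ2 and variance α_r²/τ. The two precisions "introduce flexibility by allowing variability to differ between new HO volume in treated subjects and untreated subjects". No parameter in the mean, the variance or the list of priors is indexed by subject.
- **Preferred version.** The untransformed model has the same structure, and "The Bayesian analysis without square root transformation is referred to as the analysis of primary interest".
- **Simulation.** SAP 1.7 draws a gamma rate per subject, Poisson counts, and then a gamma volume per region from the Table 1 mean and SD. The volume step has no subject term.

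**The concern.** A subject can contribute up to nine regions per scan, up to four post-baseline MOVE scans, and NHS scans as well. About 45 of the 80 planned MOVE subjects come from the NHS. If some subjects tend to form larger volumes than others, these values are not independent, and a model that treats them so gives θ2 too small a posterior SD. γ inherits part of that.

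The documents report no such correlation, but three features make zero an uncomfortable default:

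- The SAP's own illustration under Sensitivity Analyses has one growth event of 8000 mm³ recorded in MOVE as 4000 mm³ on each of two successive scans. The model would treat these as two independent volumes.
- SAP 1.10.1 says age may matter for the formation of new HO, yet age and sex are absent from the volume half. Any age effect on volume becomes a shared residual within subject.
- The SAP notes that a minority of subjects form large amounts of HO in a year. This is only suggestive, since more regions or larger regions would also explain it.

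At stake is the width of the interval for γ, and P(γ<1), in the third interim analysis (IA3). The SAP designates IA3 as the final efficacy analysis and reports it in the interim CSR for the marketing applications.

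**Working it through.** **1. How concentrated are the volumes?** Take the SAP 1.7 rate distribution, gamma with mean 0.707 and SD 1.11 per year, over 2 years.

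- Shape k = 0.707²/1.11² = 0.406; mean count μ = 1.414.
- P(0) = (k/(k+μ))^k = (0.406/1.820)^0.406 = 0.544.
- P(1) = k·μ/(k+μ)·P(0) = 0.406 × 0.777 × 0.544 = 0.171.
- Share of volumes from subjects with two or more: 1 − 0.171/1.414 = 0.88.

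So about 54% of subjects contribute no volume, and 88% of volumes come from subjects who contribute several.

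**2. Reproducing the plan's figures.** The SAP 1.7 steps were re-simulated with 1,000 trials per setting:

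- 90 NHS subjects (45 with scans at 1 and 1.5 years, 45 at 1 and 2 years) and 80 MOVE subjects, 45 of them in both;
- the Table 7 schedule and the stated thresholds 0.0058, 0.0103, 0.0156 and 0.0190;
- the SAP model and priors fitted by MCMC.

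Simplifications: no sex or age terms, ten region sites taken from Table 1, and the 1.5-year NHS subjects taken as the crossovers.

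With independent volumes and the square root, the cumulative null success rate was 0.003, 0.010, 0.017, 0.020, against 0.006, 0.010, 0.013, 0.021 in SAP Table 2. These agree within Monte Carlo error (about 0.004 at the final look). Final power was 0.873 (square root) and 0.959 (untransformed) against the stated 0.922. This is not an exact match, but region mapping and crossover handling are not fully specified, so it is not evidence of an error in the plan.

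**3. Adding within-subject volume correlation.** Volumes were linked within subject by a Gaussian copula that keeps the Table 1 margins. The latent correlation ρ is an assumption. The ratio below is the SD across trials of the posterior mean, divided by the average posterior SD, on the log scale under no effect. A value of 1.00 means the stated width is right.

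| Scale | Subject effect | ρ | θ2 ratio | γ ratio | Cumulative type I error |
|---|---|---|---|---|---|
| Square root | shared | 0 | 1.00 | 1.05 | 0.020 |
| Square root | shared | 0.3 | 1.31 | 1.11 | 0.025 |
| Square root | shared | 0.6 | 1.48 | 1.18 | 0.024 |
| Square root | redrawn between studies | 0.3 | 1.49 | 1.12 | 0.028 |
| Square root | redrawn between studies | 0.6 | 1.79 | 1.24 | 0.038 |
| Untransformed | shared | 0 | 1.05 | 1.08 | 0.017 |
| Untransformed | shared | 0.3 | 1.27 | 1.17 | 0.021 |
| Untransformed | shared | 0.6 | 1.44 | 1.26 | 0.034 |

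Monte Carlo SE of the error rates is 0.004–0.006.

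**4. Why γ suffers less than θ2.** The two halves share no parameters, so Var(log γ) = Var(log θ1) + Var(log θ2). At ρ = 0 the posterior SDs of log θ2 and log γ are 0.079 and 0.189 (square root), and 0.142 and 0.223 (untransformed). The θ2 share of the variance is therefore 0.079²/0.189² = 17% and 0.142²/0.223² = 41%. Counts dominate, and the untransformed analysis is the more exposed.

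**5. Effect of one shared subject term on volume.** Null, final analysis only, 400 trials per row; posterior SD / true SD of log γ.

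| Setting | SAP model | With subject term |
|---|---|---|
| Square root, ρ = 0 | 0.189 / 0.189 | 0.192 / 0.187 |
| Square root, ρ = 0.6, shared | 0.189 / 0.211 | 0.186 / 0.194 |
| Untransformed, ρ = 0.6, shared | 0.222 / 0.289 | 0.206 / 0.247 |
| Square root, ρ = 0.6, redrawn | 0.189 / 0.232 | 0.190 / 0.253 |
| Untransformed, ρ = 0.6, redrawn | 0.221 / 0.291 | 0.221 / 0.358 |

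When the effect is shared, the term mainly lowers the true error, because crossover subjects act partly as their own controls. When the effect differs between studies, a single shared term does not repair the calibration.

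**The case against.** The case on the other side is substantial.

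- **The correlation is unknown.** The documents give no value, and at zero the θ2 posterior is about correctly sized. This stands, and it makes the point conditional.
- **The variance assurance concerns counts.** The negative binomial statement does refer to the number of body regions. The sentence before it, on measurements from the same subject, is broader and can be read as covering the whole model.
- **Other analyses handle the clustering.** The wLME model, the SAP's alternative analysis of primary interest, has a subject random effect and uses one record per study. The GEE analysis uses the empirical variance and is the named example of the post-lock comparison with the NHS. Both are useful checks on the conclusion, but neither corrects the P(γ<1) reported from the Bayesian model.
- **No threshold applies any longer.** After the futility crossing, efficacy results are supplied without success or futility limits. This lowers the stakes for a formal decision, but the Bayesian result is still the headline for IA3.
- **A separate simulation report is promised** (SAP 1.7). It may cover correlated volumes; nothing in the SAP says that it does.

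**Conclusion.** The structural point holds. The volume half carries no subject term in either version of the model, the correlation statement is valid for counts only, and the simulation behind SAP Table 2 sets the correlation to zero by construction.

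The size is conditional. At an assumed ρ of 0.3 to 0.6 with shared effects, the true SD is 27–48% above the stated one for log θ2 and 11–26% above for log γ. Of the latter, 5–8% is there without any correlation. Cumulative type I error moves from 0.017 to 0.034 untransformed at ρ = 0.6, and from 0.020 to 0.024 on the square-root scale, or to 0.038 there if effects are redrawn between studies. These rest on the copula, on the simplifications listed above, and on 1,000 trials per setting.

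A reader might infer three stronger things that the material does not support:

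- That the posterior for γ is too narrow as a matter of fact. This needs a positive correlation that the documents do not report.
- That type I error is seriously inflated. The rise is modest, and at ρ = 0.3 it is within Monte Carlo error of the value at zero when effects are shared.
- That a corrected model would give wider intervals and so weaken the result. The posterior SD hardly changed, and it fell in some settings.

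**What to change.** 1. In SAP 2.4.4, state that the subject-level rate accounts for within-subject correlation of the counts only.
2. Refit the IA3 Bayesian model, with and without the square root, adding a subject-level multiplicative effect and a subject-by-study term to the mean volume, with weakly informative priors on their SDs. Report γ, P(γ<1) and the estimated within-subject SD beside the planned analysis. The second term is needed because a single shared effect failed when effects differed between studies. The two-term model was not simulated here, so its calibration should be checked in step 3.
3. Add correlated-volume scenarios to the separate simulation report, with effects both shared and redrawn between studies.

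The cost is a little extra model fitting and a post-hoc, post-unblinding label, so this belongs as a sensitivity analysis and not a replacement. At zero correlation, one shared subject term costs almost nothing (posterior SD of log γ 0.189 to 0.192 on the square-root scale).

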### 6.3 Randomization and Blinding

This is an open-label study and does not involve randomization or study drug blinding.

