1.10 Statistical Modifications to the Statistical Analysis Plan

1.10.1 Statistical Modifications to the Statistical Analysis Plan, V1.0

The primary and secondary efficacy analyses described in Protocol Amendment 1 do not include explanatory covariates. Because recent studies – Clementia’s NHS as well as other studies – suggest that age may be important for flare-up rate and the formation of new HO, age (<18, ≥18 years) and additional categorical variable sex (Male, Female) is included in the primary and secondary efficacy analyses.

The analysis of the secondary endpoints proportion of subjects with any new HO and number of body regions with new HO will both be conducted using the Bayesian compound Poisson model used in the primary efficacy analysis; in fact, the inference is identical for these two secondary endpoints. Within the compound Poisson model, $\theta_{1,1} < 1$ implies both a lower proportion of subjects with any new HO and a smaller number of body regions with new HO for palovarotene-treated subjects.

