Missing timepoints for subjects, i.e., assessments not conducted, assessments conducted but not evaluable for the presence of HO or volume of HO, or assessments for which HO volume for at least 50% of body regions is not evaluable or not available, will not be imputed. Body regions with non-evaluable HO volume at a timepoint will be represented as having no new HO and the volumes will be set to zero in the analysis.

As described in the MOVE and NHS Independent Review Charter, adjudication is by timepoint. When adjudicated, analysis will use the adjudication assessment of volume of new HO. When not adjudicated, the average of the two readers' amounts of HO for each body region will be used, assigning a volume of 0 mm^3 if the reader does not measure due to the qualitative assessment of no new HO.

Using the Bayesian compound Poisson model described above, the efficacy ratio γ is calculated as the treatment effect on the mean number of body regions with new HO, $\theta_{1,1}$, multiplied by the

treatment effect on new HO volume conditional on new HO occurring, $\theta_{2,1}$, expressed as $\gamma = \theta_{1,1} * \theta_{2,1}$. Random samples generated via Gibbs sampling from the posterior distribution of $\theta_{1,1}$ and $\theta_{2,1}$ will be used to compute the posterior probability that $\gamma < 1$ to determine statistical significance.

Additional Analyses

The primary efficacy analysis described above will be repeated without the square-root transformation. As noted by the DMC after the second interim analysis, using the square-root transformation of the data in the primary analysis was impactful in that it appeared to have moved the statistical conclusion from significant therapeutic benefit to showing futility of the treatment.

Furthermore, as is explained later in this section, the square-root transformation together with the more frequent WBCT efficacy assessments in MOVE relative to NHS seem to introduce a bias against palovarotene in the primary analysis.

Also, with its square-root transformation reducing the influence of subjects with unusually large amounts of new HO, the primary analysis is expected to be less powerful relative to the analysis without the square-root transformation if an effect of palovarotene is to reduce the chance of catastrophic HO as is suggested in the results observed thus far in MOVE (and was also observed in post-hoc analyses of flare-up-based imaging endpoints in earlier studies).

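### Age and sex adjust only the count half of the primary Bayesian model, so the volume effect θ2 is adjusted for body region alone

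*SAP*

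**What the plan says.** SAP 2.4.4 (Primary Analysis) models new HO in two halves.

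- **Count half.** The log rate of regions with new HO contains a subject-level rate λ_i, sex (X1,i) and age at scan (X2,ij, under 18 or not). The stated purpose is: "Covariates are included in the analysis of the number of body regions with new HO to adjust for potential explained differences in the rate". The covariate effects "are multiplicative effects of sex and age on the rate of body regions with new HO".
- **Volume half.** Given new HO in region r, the mean is α × α_r × θ2 and the variance is α_r²/τ. The α_r "are region-specific variables that contribute to the mean of new HO and the variance". No age, sex or subject term appears. θ2 "is the multiplicative effect of palovarotene treatment on the new HO volume conditional on new HO occurring".

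The two effects are multiplied, γ = θ1 × θ2, and the posterior probability that γ < 1 is the test quantity. The untransformed model under Additional Analyses, which the sponsor calls the analysis of primary interest, has the same volume mean.

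SAP 1.10.1 explains why covariates were added to the covariate-free protocol model: recent studies "suggest that age may be important for flare-up rate and the formation of new HO". Protocol 6.3 states: "This is an open-label study and does not involve randomization or study drug blinding".

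**The concern.** Without randomisation, covariate adjustment is one of the main protections for the headline estimate. Here it reaches θ1 but not θ2. If volume given new HO varies with age or sex, and the two studies differ in age or sex mix among regions with new HO, the difference is read as a drug effect on volume.

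The overlap between studies does not help. SAP 1.7 assumes about 45 of 90 NHS subjects enter MOVE, but the term that links a subject's own scans, λ_i, is also only in the count half.

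θ2 carries much of the result. The design effect in SAP 1.7 is 30% fewer regions and 50% less volume. On the log scale that is ln 0.7 = −0.357 and ln 0.5 = −0.693, total −1.050, so about two-thirds (0.693/1.050) sits in θ2. The square-root choice, which the DMC thought had moved the conclusion from benefit to futility, changes only the volume likelihood and its priors.

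**Working it through.** **1. The plan's own figure.** SAP Table 2 gives a type I error of 0.021 and power of 0.922 at the final analysis. I simulated the SAP 1.7 recipe (90 NHS and 80 MOVE subjects, 45 in both, six-monthly MOVE scans, Table 1 volumes, square-root scale, stated thresholds). I used a Laplace approximation to the posterior instead of Gibbs sampling.

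- Type I error: 0.022 (1,000 runs), which agrees.
- Power: 0.882 with the SD of 1.11 read as the SD of the gamma rate (1,000 runs); 0.927 with nine regions and 1.11 read as the SD of observed counts (450 runs).

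Table 2 was simulated with no age or sex effect on volume and no imbalance. Its statement that type I error is maintained therefore does not test this gap.

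**2. Closed form for θ2 with no drug effect.** Let k be the ratio of under-18 to adult volume given new HO, and let p0 and p1 be the under-18 shares of new-HO regions in NHS and MOVE. Then

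θ2(null) = [1 + p1(k − 1)] / [1 + p0(k − 1)].

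On the square-root scale, replace k by √k. The documents give neither k nor the shares, so all three are assumptions.

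| k | p0 (NHS) | p1 (MOVE) | Untransformed | Square root |
|---|---|---|---|---|
| 1.5 | 0.60 | 0.50 | 1.25/1.30 = 0.96 | 1.112/1.135 = 0.98 |
| 3 | 0.70 | 0.50 | 2.00/2.40 = 0.83 | 1.366/1.512 = 0.90 |
| 1.5 | 0.50 | 0.60 | 1.30/1.25 = 1.04 | 1.135/1.112 = 1.02 |
| 3 | 0.50 | 0.70 | 2.40/2.00 = 1.20 | 1.512/1.366 = 1.11 |

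With k = 1 or p0 = p1 the ratio is exactly 1.

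**3. Check by simulation, with different assumptions.** No drug effect; NHS 50% children; new MOVE subjects 90% children (deliberately large); R = adult/child volume ratio; final look at 0.0190; 500 or 600 runs per row.

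| Scale | R | θ2 | False success | θ2 with age in volume mean |
|---|---|---|---|---|
| Untransformed | 1.5 | 0.931 | 4.0% | 1.00 |
| Untransformed | 2 | 0.883 | 5.8% | 1.00 |
| Untransformed | 3 | 0.820 | 10.0% | 1.00 |
| Untransformed | 0.5 | 1.118 | 0.7% | 1.00 |
| Square root | 1.5 | 0.966 | 1.8% | 1.00 |
| Square root | 2 | 0.942 | 3.8% | 1.00 |
| Square root | 3 | 0.908 | 5.2% | 1.00 |
| Square root | 0.5 | 1.060 | 1.0% | 1.00 |

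The closed form agrees. If crossovers keep the NHS mix, the MOVE child share is (45 × 0.5 + 35 × 0.9)/80 = 0.675. R = 2 then gives (0.675 + 0.325 × 2)/(0.5 + 0.5 × 2) = 1.325/1.5 = 0.883.

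With age in the volume mean, false success returned to 1.6–2.0% in every scenario. When age did not affect volume, final-look power with the extra term was 0.881, against 0.882 cumulative power without it.

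**The case against.** **Other planned analyses.** SAP 2.4.4 plans, after the third interim, a covariate-extended Bayesian run with a matching wLME (including age and sex), propensity-quartile analyses, a wLME in subjects followed in both studies, and Bayesian age and age-by-sex subgroups. It also reports a caliper-matched comparison. SAP Table 8 adds younger and older subsets. The wLME models total annualised volume, so its covariates act on the whole outcome, and age subgroups estimate θ2 within strata. This stands as partial cover. However, none of these corrects the headline γ, and the text for the two Bayesian covariate runs does not say which half receives the covariates.

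**Size and sign.** A reader might infer that γ is biased in the drug's favour. The documents do not support that. SAP 1.10.1 speaks of flare-up rate and formation of new HO, not of volume once new HO exists, and no age mix is given. The tables above give θ2 on either side of 1, depending on assumptions. Ageing between studies changes the binary age term only for subjects who pass 18, so crossover alone is weak evidence of a large shift.

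**Error rates.** A reader might also infer an inflated false-positive rate for the trial. SAP 2.4.4 no longer applies success or futility thresholds, so the simulated rates show how evidence could be distorted and do not describe a live decision.

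**Unadjusted.** It would be too strong to call θ2 wholly unadjusted: body region enters through α_r.

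**Conclusion.** The structural point holds and follows from the model equations alone: age and sex adjust θ1 and not θ2, in both the square-root and the untransformed model. Differences between studies in age or sex mix that relate to volume given new HO enter γ.

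The size and direction cannot be determined from the documents. A null θ2 of 0.83 to 0.96 untransformed (about 0.90 to 0.98 on the square-root scale) rests on assumed under-18 volumes 1.5 to 3 times larger and an assumed under-18 share 10 to 20 points lower in MOVE. Reversing the imbalance reverses the bias.

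Nor do the documents show that confounding explains why the two scales disagree. The disagreement must come through θ2, because the count model is common to both. The SAP offers other explanations, namely the visit schedules and the influence of very large volumes, and nothing in it separates these from an age effect.

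**What to change.** Keep the specified models as they are. The sponsor has been unblinded since the second interim (SAP 1.4 and 1.10.2), so replacing the primary model now would be a further post-hoc change to it. Instead:

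1. Add to SAP 2.4.4, labelled post hoc and reported beside the specified results, a run of both the square-root and the untransformed model with the volume mean multiplied by exp(β3·X1,i + β4·X2,ij), priors N(0, 2²), on the third-interim data.
2. State under Sensitivity Analyses that the additional covariates and the propensity quartiles enter both the count and the volume halves of the Bayesian model.

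Cost: two extra parameters in existing R code and no new data. It also needs a rerun that SAP 3.3 does not currently plan, since interim-report analyses are not to be repeated for the final report, and it adds one more post-hoc analysis after unblinding.
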